Appendix 10 Management of Cobimetinib plus Atezolizumab-Associated Adverse Events (Arm A) (cont.)

Table 5 Guidelines for Managing Cobimetinib-Associated Serous Retinopathy and Retinal Vein Occlusion (cont.)

Description	Management
Potential immune-mediated ocular toxicity (e.g., uveitis, iritis, episcleritis, or retinal events)	
 • For atezolizumab, Follow guidelines provided in the Appendix 11. • Continue cobimetinib as clinically indicated.

ADL = activities of daily living; RVO = retinal vein occlusion.

- ^a Grade 1: Asymptomatic or mild symptoms; clinical or diagnostic observations only; intervention not indicated.
- ^b Grade 2: Moderate; minimal, local or noninvasive intervention indicated; limiting age appropriate instrumental ADL.
- ^c Grade 3: Severe or medically significant but not immediately sight threatening; hospitalization or prolongation of existing hospitalization indicated; disabling; limiting self-care ADL.
- ^d Grade 4: Sight-threatening consequences; urgent intervention indicated; blindness (20/200 or worse) in the affected eye.

GUIDELINES FOR MANAGEMENT OF PATIENTS WHO EXPERIENCE DECREASED LEFT VENTRICULAR EJECTION FRACTION

Decreased left ventricular ejection fraction (LVEF) has been seen with cobimetinib (see Section [5.1.1.1.3](#)) and should be managed according to the guidelines in [Table 6](#).

Appendix 10 Management of Cobimetinib plus Atezolizumab-Associated Adverse Events (Arm A) (cont.)

Table 6 Recommended Dose Modifications for Cobimetinib in Patients with Left Ventricular Ejection Fraction Decrease from Baseline

Left Ventricular Ejection Fraction (LVEF) Decrease from Baseline				
Patient	LVEF Value	Recommended Action with Cobimetinib and Atezolizumab	LVEF Value following Treatment Break	Recommended Cobimetinib Daily Dose
Asymptomatic	≥ 50% (or 40%–49% and < 10% absolute decrease from baseline)	Continue atezolizumab and cobimetinib at current dose	NA	NA
	< 40% (or 40%–49% and ≥ 10% absolute decrease from baseline)	Interrupt cobimetinib treatment for 2 weeks Continue atezolizumab as clinically indicated	< 10% absolute decrease from baseline	First occurrence: 40 mg
				Second occurrence: 20 mg
				Third occurrence: permanent discontinuation
< 40% (or ≥ 10% absolute decrease from baseline)	Permanent discontinuation			
Symptomatic	NA	Interrupt cobimetinib treatment for 4 weeks	Asymptomatic and < 10% absolute decrease from baseline	First occurrence: 40 mg
				Second occurrence: 20 mg
				Third occurrence: permanent discontinuation
		Consider withholding atezolizumab. Discuss with Medical Monitor regarding resumption of atezolizumab.	Asymptomatic and < 40% (or ≥ 10% absolute decrease from baseline)	Permanent discontinuation
Cardiology consultation is strongly recommended.	Symptomatic regardless of LVEF	Permanent discontinuation		

LVEF = left ventricular ejection fraction; NA = not applicable.

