4.5.9 Left Ventricular Ejection Fraction

All patients will require evaluation of LVEF at screening, and only patients receiving cobimetinib (Arm A) will require subsequent evaluations of LVEF.

Evaluation of LVEF by ECHO or MUGA must be performed at the following timepoints:

- Screening
- Day 1 of Cycle 2 (± 1 week)
- Day 1 of every three treatment cycles and starting at Cycle 5 and thereafter (± 2 weeks)
- The treatment discontinuation visit evaluation of LVEF does not need to be performed at the treatment discontinuation visit if an evaluation has been performed within the last 12 weeks and there are no clinically significant findings and/or changes from baseline.
- All patients restarting treatment with a dose reduction of cobimetinib because of a decrease in LVEF should have LVEF measurements taken after approximately 2 weeks, 4 weeks, 10 weeks, and 16 weeks, and then resume monitoring of LVEF every three treatment cycles.

Any patient who develops clinical signs or symptoms suspicious of cardiac failure should undergo an LVEF assessment. Evaluation of LVEF must be performed using the same method (ECHO or MUGA) for each patient. It is strongly encouraged that the same laboratory and operator perform ECHO or MUGA scans for each individual patient. Investigators must be aware of local institution regulations regarding repeat MUGA scans. The repeat administration of radioisotopes is limited in some nuclear medicine laboratories, and some patients in this study could require monitoring on four or more occasions.

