5.1.5 Management of Patients Who Experience Specific Adverse Events

5.1.5.1 Cobimetinib Dose Modifications

General dose modification for cobimetinib is provided in [Table 3](#). Dose modification for specific adverse events is provided in [Appendix 10](#). After dose reduction, consideration may be given to allow for dose escalation of cobimetinib by a maximum of one dose level (20 mg) increments following resolution of the adverse event that resulted in dose modification, provided there are no safety concerns.

Table 3 Recommended Cobimetinib Dose Modifications

Grade (NCI CTCAE) ^a	Recommended Cobimetinib Dose
Grade 1 or Grade 2 (tolerable)	No dose reduction. Maintain cobimetinib at the same dose of 60 mg QD (3 tablets).
Grade 2 (intolerable) or Grade 3 or 4 (any)	
First appearance	Interrupt treatment until Grade ≤ 1: restart treatment at 40 mg QD (2 tablets).
Second appearance	Interrupt treatment until Grade ≤ 1: restart treatment at 20 mg QD (1 tablet).
Third appearance	Consider permanent discontinuation.

NCI CTCAE=National Cancer Institute Common Terminology Criteria for Adverse Events; QD=once a day.

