Appendix 10 Management of Cobimetinib plus Atezolizumab-Associated Adverse Events (Arm A)

Note: For information regarding management of atezolizumab-associated adverse events, please refer to [Appendix 11](#).

Guidelines for Management of Cobimetinib plus Atezolizumab Adverse Events

Event	Action to Be Taken
General guidance for dose modifications and treatment delays and discontinuation	
 • There will be no dose modifications for atezolizumab. • If atezolizumab is withheld and corticosteroids are initiated for an atezolizumab-related toxicity, corticosteroids must be tapered over ≥ 1 month to ≤ 10 mg/day oral prednisone or equivalent before atezolizumab can be resumed.^{a, b, c} 
The dose of cobimetinib can be reduced by 20 mg (one dose level) up to two times (i.e., from 60 mg to 40 mg and then from 40 mg to 20 mg). If further dose reduction is indicated after two dose reductions, the patient must discontinue cobimetinib but may continue treatment with atezolizumab at the investigator's discretion.
 
 • If cobimetinib is withheld for > 28 days because of toxicity, the patient should be discontinued from cobimetinib, unless resumption of treatment is approved by the Medical Monitor after discussion with the investigator. • After dose reduction, consideration may be given to allow for dose escalation of cobimetinib by a maximum of one dose level following resolution of the adverse event that resulted in dose modification, provided there are no safety concerns. • If atezolizumab is withheld for > 12 weeks because of toxicity, the patient should be discontinued from atezolizumab, unless resumption of treatment is approved by the Medical Monitor after discussion with the investigator.
IRRs, CRS, anaphylaxis, and hypersensitivity reaction	
 • Guidelines for management of IRRs and CRS are provided in the Atezolizumab Investigator's Brochure and Appendix 11 • For anaphylaxis precautions, see Appendix 7. • For severe hypersensitivity reactions, permanently discontinue all study treatment.

CRS = *cytokine-release syndrome*; IRR = infusion-related reaction.

^a If corticosteroids have been initiated, they must be tapered over ≥ 1 month to ≤ 10 mg/day oral prednisone or equivalent before atezolizumab can be resumed.

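### Protocol Appendix 10, Table 6 (LVEF falls): read literally, it raises cobimetinib from 20 mg to 40 mg in a patient already reduced for another toxicity, and its restart and stop rows overlap when baseline LVEF is below 50%

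*Protocol*

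**What the plan says.** Section 5.1.5.1 gives general cobimetinib dose changes in its Table 3 and then directs the reader elsewhere for particular toxicities: "Dose modification for specific adverse events is provided in" Appendix 10. The text introducing Table 6 of that appendix sends LVEF decreases to Table 6.

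Table 6 gives absolute restart doses: "First occurrence: 40 mg", 20 mg at the second occurrence, permanent stop at the third. It does not mention the dose before the event. In the asymptomatic block, cobimetinib is interrupted if LVEF is below 40%, or is 40% to 49% with a fall of at least 10 points. After the break, one row allows restart if the fall from baseline is under 10 points, with no minimum LVEF. Another row requires permanent discontinuation if LVEF is below 40% or the fall is 10 points or more. The symptomatic block repeats this pair of rows for patients whose symptoms have cleared.

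Three other places bear on the dose:

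- The general guidance opening Appendix 10: "The dose of cobimetinib can be reduced by 20 mg (one dose level) up to two times", and "If further dose reduction is indicated after two dose reductions, the patient must discontinue cobimetinib".
- The condition on re-escalation in Section 5.1.5.1, repeated in Appendix 10: at most one level, "following resolution of the adverse event that resulted in dose modification, provided there are no safety concerns".
- Section 4.5.9, which ties extra LVEF checks at about 2, 4, 10 and 16 weeks to "All patients restarting treatment with a dose reduction of cobimetinib because of a decrease in LVEF". Routine checks are on "Day 1 of every three treatment cycles and starting at Cycle 5 and thereafter".

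**The concern.** Left ventricular dysfunction is listed in Section 5.1.1.1 as an important identified risk of cobimetinib. A table for managing it should not be readable as raising the dose after a cardiac event, nor give two opposite orders for the same LVEF value. Sites are directed to Table 6 for this event, so it is the table they would have open.

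There is a knock-on effect on monitoring. The extra LVEF checks are written for patients restarting at a reduced dose. Read literally, a patient restarted at a higher dose would stay on the routine schedule.

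**Working it through.** No sample size, power or alpha figure is involved, so there is no plan figure to reproduce. The check is to apply the printed rules case by case.

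**Restart dose after a first LVEF occurrence.** Change = Table 6 dose minus dose before the event.

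| Dose before event | Table 6 dose | Change | General guidance, if a reduction is indicated |
|---|---|---|---|
| 60 mg | 40 mg | 40 − 60 = −20 mg | 40 mg |
| 40 mg | 40 mg | 40 − 40 = 0 mg | 20 mg |
| 20 mg | 40 mg | 40 − 20 = +20 mg | discontinue |

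Only the last row is a rise. It arises when LVEF recovers to within 10 points of baseline after the break. The re-escalation clause does not cover it: that clause is discretionary and excludes cases with safety concerns, and a new LVEF fall is one.

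**Post-break rows.** Let b be baseline LVEF and p the post-break value.

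- Restart: b − p < 10.
- Stop: p < 40, or b − p ≥ 10.
- Both apply when b − 10 < p < 40. Some p satisfies this only if b < 50.

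In whole percents:

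- b = 45: p = 36 to 39
- b = 46: p = 37 to 39
- b = 47: p = 38 to 39
- b = 48: p = 39
- b = 49 or more: none

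At a resolution of 0.1, the highest baseline with an overlap is 49.8% (p = 39.9, fall 9.9).

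Example: baseline 47%, on treatment 36%. Since 36 < 40, cobimetinib is interrupted. After the break LVEF is 38%. The fall is 47 − 38 = 9, so the restart row applies; 38 < 40, so the stop row applies too.

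**Can such a patient enrol?** The LVEF exclusion (synopsis and Section 4.1.2.3.1) uses the lower of the site's lower limit of normal and 50%. With a site limit of 50% or more, every eligible baseline is at least 50% and there is no overlap. With a limit of 45% (assumed for illustration), whole-number baselines of 45% to 48% are exposed.

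**Rough size of the dose-rise case.** Section 5.1.1.1.3 reports Grade 2 or 3 LVEF reductions in 8.5% of patients on cobimetinib plus vemurafenib, with 62% of events improved or resolved.

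- 225 × 0.085 = 19.1 Arm A patients
- 19.1 × 0.62 = 11.9 who might restart
- If 2% to 10% of these were already at 20 mg (assumed; the documents give no figure): 11.9 × 0.02 = 0.2 to 11.9 × 0.10 = 1.2 patients

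**The case against.** The strongest reply is that the protocol, taken as a whole, does not order an escalation. Table 6 is headed as recommended modifications and sits under general guidance that works in steps down. The re-escalation condition bars an increase when there is a safety concern, and Section 4.5.9 speaks of restarting at a reduced dose. A site reading all of this would not go from 20 mg to 40 mg. That stands: this is an unresolved conflict between rules, not an instruction to escalate. But the general guidance and Table 6 are both in Appendix 10, so the pointer from Section 5.1.5.1 does not rank them, and no other text does.

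On the overlap, LVEF below 40% is itself the interruption trigger for an asymptomatic patient, so stopping is the sensible reading at 38%. That also stands, and it shows which row should win. The restart row still says otherwise.

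A reader might also infer that the same-dose restarts in Table 6 (40 mg at a first event, 20 mg at a second) are errors. The documents do not support that. The general guidance says the dose can be reduced and requires stopping only where further reduction is indicated. Elsewhere in Appendix 10, the rows for Grade 2 pneumonitis and for suspected Stevens-Johnson syndrome or toxic epidermal necrolysis resume cobimetinib with no stated reduction, although nine other rows restart one level down.

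Nor does the shared layout justify rewriting Table 3 of Section 5.1.5.1. Mandatory stopping at 20 mg in its first-appearance cell would be stricter than its third-appearance cell, which only asks that discontinuation be considered.

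**Conclusion.** Both defects are present in Table 6. The dose ladder does not provide for a patient already at 20 mg and, taken alone, doubles that patient's dose after a first LVEF event. The restart and stop rows give opposite instructions for some post-break values when baseline LVEF is below 50%.

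The reach is small. The estimate of 0.2 to 1.2 patients assumes that the rate seen with the vemurafenib combination carries over, that Grade 2 or 3 reductions match Table 6's trigger, that improvement or resolution means recovery to within 10 points, and that 2% to 10% of such patients are at 20 mg. None of these is established in the documents. The overlap cannot be sized because no site lower limits are given. No endpoint, analysis or statistical figure changes. This is a minor patient-safety correction, worth making because the dose error points towards more drug after a cardiac event.

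**What to change.** Change Table 6 only, in both the asymptomatic and symptomatic blocks:

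1. Make the restart condition an LVEF of at least 40% together with a fall from baseline of less than 10 points. It then becomes the exact complement of the stop condition, so no value meets both and none meets neither.
2. Add to the restart-dose cells: *the restart dose must never exceed the dose before interruption; if the patient was already at 20 mg, do not increase, and discuss discontinuation with the Medical Monitor per the general guidance.*

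Leave Table 3 of Section 5.1.5.1 as it is, and keep permanent discontinuation at the third LVEF occurrence.

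The cost is a few table cells, with no new assessments or patients. SAP Section 2.5 says the study will be terminated early, so if no further amendment is planned, a dosing clarification to sites with patients still on cobimetinib would be enough.

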Appendix 10 Management of Cobimetinib plus Atezolizumab-Associated Adverse Events (Arm A) (cont.)

GUIDELINES FOR MANAGEMENT OF PATIENTS WHO EXPERIENCE ELEVATED CPK AND RHABDOMYOLYSIS

Elevated CPK has been reported with cobimetinib (see Section 5.1.1.1.4) and should be managed according to the guidelines in Table 7.

Table 7 Recommended Dose Modifications for Cobimetinib and Atezolizumab in Patients with CPK Elevations and Rhabdomyolysis

Event	Action to Be Taken
Rhabdomyolysis or CPK elevation	
General guidance	
 • Rule out cardiac cause (check ECG, serum cardiac troponin, and CPK-isoforms M and B fraction) and rule out rhabdomyolysis (clinical examination; serum creatinine, potassium, calcium, phosphorus, uric acid, and albumin; and urine myoglobin). • Assess patient for any history of strenuous physical activity, blunt trauma, or recent intramuscular injections.
For Grade ≤ 3 CPK elevations that are asymptomatic and deemed not clinically significant	
 • Cobimetinib and atezolizumab dosing does not need to be modified or interrupted to manage asymptomatic Grade ≤ 3 CPK elevations. • Recheck CPK at least once a week.
For Grade 4 CPK elevations that are asymptomatic and deemed not clinically significant	
 • Interrupt cobimetinib and atezolizumab treatment. • If improved to Grade ≤ 3 within 4 weeks, restart cobimetinib at a dose reduced by 20 mg, if clinically indicated. • If CPK elevations do not improve to Grade ≤ 3 within 4 weeks following dose interruption, permanently discontinue cobimetinib treatment. • Resumption of atezolizumab may be considered in patients who are deriving benefit.
Rhabdomyolysis or symptomatic CPK elevations	
 • Interrupt cobimetinib and atezolizumab treatment. • If severity is improved by at least one grade and symptoms resolve within 4 weeks, restart cobimetinib at a dose reduced by 20 mg, if clinically indicated. • If rhabdomyolysis or symptomatic CPK elevations do not improve within 4 weeks, permanently discontinue cobimetinib treatment • Resumption of atezolizumab may be considered in patients who are deriving benefit after discussion with the Medical Monitor.

Appendix 10 Management of Cobimetinib plus Atezolizumab-Associated Adverse Events (Arm A) (cont.)

GUIDELINES FOR MANAGEMENT OF PATIENTS WHO EXPERIENCE HEMORRHAGE

Hemorrhage has been reported with cobimetinib (see Section 5.1.1.1.1) and should be managed according to the guidelines in Table 8.

Table 8 Recommended Dose Modifications in Patients with Hemorrhage

Event	Action to Be Taken
Hemorrhage	
Grade 3 hemorrhage	
 • Interrupt cobimetinib treatment. There are no data on the effectiveness of cobimetinib dose modification for hemorrhage events. Clinical judgment should be applied when considering restarting cobimetinib treatment. • Continue atezolizumab treatment.
Grade 4 hemorrhage or any grade cerebral hemorrhage	
 • Interrupt cobimetinib treatment. Permanently discontinue cobimetinib for hemorrhage events attributed to cobimetinib. • Continue atezolizumab treatment.
Grade 3 or 4 or intolerable Grade 2 treatment-related toxicities not described above and Table 3 (dose modifications for cobimetinib)	
 • Withhold all study treatment. • If event resolves to Grade 1 or better within 12 weeks, resume atezolizumab at fixed dose. If not, permanently discontinue atezolizumab.^{a, b, c} • If event resolves to Grade 1 or better within 28 days, resume cobimetinib with dose reduced by one level. If not, permanently discontinue cobimetinib.

^a If corticosteroids have been initiated, they must be tapered over ≥ 1 month to ≤ 10 mg/day oral prednisone or equivalent before atezolizumab can be resumed.

^b Atezolizumab may be withheld for a period of time beyond 105 days to allow for corticosteroids to be reduced to ≤ 10 mg/day oral prednisone or equivalent. The acceptable length of the extended period of time must be agreed upon by the investigator and the Medical Monitor.

^c Resumption of atezolizumab may be considered in patients who are deriving benefit and have fully recovered from the immune-mediated event. Patients can be rechallenged with atezolizumab only after approval has been documented by both the investigator (or an appropriate delegate) and the Medical Monitor.

Appendix 11

Risks Associated with Atezolizumab and Guidelines for Management of Adverse Events Associated with Atezolizumab

Toxicities associated or possibly associated with atezolizumab treatment should be managed according to standard medical practice. Additional tests, such as autoimmune serology or biopsies, should be used to evaluate for a possible immunogenic etiology, *when clinically indicated*.

Although most immune-*mediated* adverse events observed with *atezolizumab* have been mild and self-limiting, such events should be recognized early and treated promptly to avoid potential major complications. Discontinuation of atezolizumab may not have an immediate therapeutic effect, and in severe cases, immune-*mediated* toxicities may require acute management with topical corticosteroids, systemic corticosteroids, or other immunosuppressive agents.

The investigator should consider the benefit–risk balance *for* a given patient prior to further administration of atezolizumab. In patients who have met the criteria for permanent discontinuation, resumption of atezolizumab may be considered if the patient is deriving benefit and has fully recovered from the immune-*mediated* event. Patients can be re-challenged with atezolizumab only after approval has been documented by both the investigator (or an appropriate delegate) and the Medical Monitor.

DOSE MODIFICATIONS

There will be no dose modifications for atezolizumab in this study.

TREATMENT INTERRUPTION

Atezolizumab treatment may be temporarily suspended in patients experiencing toxicity considered to be related to study treatment. If corticosteroids are initiated for treatment of the toxicity, they must be tapered over ≥ 1 month to ≤ 10 mg/day oral prednisone or equivalent before atezolizumab can be resumed. If atezolizumab is withheld for > 12 weeks after event onset, the patient will be discontinued from atezolizumab. However, atezolizumab may be withheld for > 12 weeks to allow for patients to taper off corticosteroids prior to resuming treatment. Atezolizumab can be resumed after being withheld for > 12 weeks if the Medical Monitor agrees that the patient is likely to derive clinical benefit. Atezolizumab treatment may be suspended for reasons other than toxicity (e.g., surgical procedures) with Medical Monitor approval. The investigator and the Medical Monitor will determine the acceptable length of treatment interruption.

Appendix 11

Risks Associated with Atezolizumab and Guidelines for Management of Adverse Events Associated with Atezolizumab (cont.)

MANAGEMENT GUIDELINES

PULMONARY EVENTS

Dyspnea, cough, fatigue, hypoxia, pneumonitis, and pulmonary infiltrates have been associated with the administration of atezolizumab. Patients will be assessed for pulmonary signs and symptoms throughout the study and will also have computed tomography (CT) scans of the chest performed at every tumor assessment.

All pulmonary events should be thoroughly evaluated for other commonly reported etiologies such as pneumonia or other infection, lymphangitic carcinomatosis, pulmonary embolism, heart failure, chronic obstructive pulmonary disease, or pulmonary hypertension. Management guidelines for pulmonary events are provided in [Table 1](#).

Appendix 11

Risks Associated with Atezolizumab and Guidelines for Management of Adverse Events Associated with Atezolizumab (cont.)

Table 1 Management Guidelines for Pulmonary Events, Including Pneumonitis

Event	Management
Pulmonary event, Grade 1	
 • Continue atezolizumab and monitor closely. • Re-evaluate on serial imaging. • Consider patient referral to pulmonary specialist.
Pulmonary event, Grade 2	
 • Withhold atezolizumab for up to 12 weeks after event onset.^a • Refer patient to pulmonary and infectious disease specialists and consider bronchoscopy or BAL. • Initiate treatment with 1–2 mg/kg/day oral prednisone or equivalent. • If event resolves to Grade 1 or better, resume atezolizumab.^b • If event does not resolve to Grade 1 or better while withholding atezolizumab, permanently discontinue atezolizumab and contact Medical Monitor.^c • For recurrent events, treat as a Grade 3 or 4 event.
Pulmonary event, Grade 3 or 4	
 • Permanently discontinue atezolizumab and contact Medical Monitor.^c • Bronchoscopy or BAL is recommended. • Initiate treatment with 1–2 mg/kg/day oral prednisone or equivalent. • If event does not improve within 48 hours after initiating corticosteroids, consider adding an immunosuppressive agent. • If event resolves to Grade 1 or better, taper corticosteroids over ≥ 1 month.

BAL = bronchoscopic alveolar lavage.

- ^a Atezolizumab may be withheld for a longer period of time (i.e., > 12 weeks after event onset) to allow for corticosteroids (if initiated) to be reduced to ≤ 10 mg/day oral prednisone or equivalent. The acceptable length of the extended period of time must be agreed upon by the investigator and the Medical Monitor.
- ^b If corticosteroids have been initiated, they must be tapered over ≥ 1 month to ≤ 10 mg/day oral prednisone or equivalent before atezolizumab can be resumed.
- ^c Resumption of atezolizumab may be considered in patients who are deriving benefit and have fully recovered from the immune-mediated event. Patients can be re-challenged with atezolizumab only after approval has been documented by both the investigator (or an appropriate delegate) and the Medical Monitor.

Appendix 11

Risks Associated with Atezolizumab and Guidelines for Management of Adverse Events Associated with Atezolizumab (cont.)

HEPATIC EVENTS

Immune-*mediated* hepatitis has been associated with the administration of atezolizumab. Eligible patients must have adequate liver function, as manifested by measurements of total bilirubin and hepatic transaminases, and liver function will be monitored throughout study treatment. Management guidelines for hepatic events are provided in [Table 2](#).

Patients with right upper-quadrant abdominal pain and/or unexplained nausea or vomiting should have liver function tests (LFTs) performed immediately and reviewed before administration of the next dose of study drug.

For patients with elevated LFTs, concurrent medication, viral hepatitis, and toxic or neoplastic etiologies should be considered and addressed, as appropriate.

Table 2 Management Guidelines for Hepatic Events

Event	Management
Hepatic event, Grade 1	
 • Continue atezolizumab. • Monitor LFTs until values resolve to within normal limits.
Hepatic event, Grade 2	
All events:
 
 • Monitor LFTs more frequently until return to baseline values. 
Events of > 5 days' duration:
 
 • Withhold atezolizumab for up to 12 weeks after event onset. ^a • Initiate treatment with 1–2 mg/kg/day oral prednisone or equivalent. • If event resolves to Grade 1 or better, resume atezolizumab. ^b • If event does not resolve to Grade 1 or better while withholding atezolizumab, permanently discontinue atezolizumab and contact Medical Monitor. ^c

LFT=liver function test.

^a Atezolizumab may be withheld for a longer period of time (i.e., > 12 weeks after event onset) to allow for corticosteroids (if initiated) to be reduced to ≤ 10 mg/day oral prednisone or equivalent. The acceptable length of the extended period of time must be agreed upon by the investigator and the Medical Monitor.

^b If corticosteroids have been initiated, they must be tapered over ≥ 1 month to ≤ 10 mg/day oral prednisone or equivalent before atezolizumab can be resumed.

^c Resumption of atezolizumab may be considered in patients who are deriving benefit and have fully recovered from the immune-*mediated* event. Patients can be re-challenged with atezolizumab only after approval has been documented by both the investigator (or an appropriate delegate) and the Medical Monitor.

Appendix 11

Risks Associated with Atezolizumab and Guidelines for Management of Adverse Events Associated with Atezolizumab (cont.)

Table 2 Management Guidelines for Hepatic Events (cont.)

Event	Management
Hepatic event, Grade 3 or 4	
 • Permanently discontinue atezolizumab and contact Medical Monitor. ^c • Consider patient referral to gastrointestinal specialist for evaluation and liver biopsy to establish etiology of hepatic injury. • Initiate treatment with 1–2 mg/kg/day oral prednisone or equivalent. • If event does not improve within 48 hours after initiating corticosteroids, consider adding an immunosuppressive agent. • If event resolves to Grade 1 or better, taper corticosteroids over ≥ 1 month.

LFT = liver function test.

- ^a Atezolizumab may be withheld for a longer period of time (i.e., > 12 weeks after event onset) to allow for corticosteroids (if initiated) to be reduced to ≤ 10 mg/day oral prednisone or equivalent. The acceptable length of the extended period of time must be agreed upon by the investigator and the Medical Monitor.
- ^b If corticosteroids have been initiated, they must be tapered over ≥ 1 month to ≤ 10 mg/day oral prednisone or equivalent before atezolizumab can be resumed.
- ^c Resumption of atezolizumab may be considered in patients who are deriving benefit and have fully recovered from the immune-mediated event. Patients can be re-challenged with atezolizumab only after approval has been documented by both the investigator (or an appropriate delegate) and the Medical Monitor.

GASTROINTESTINAL EVENTS

Immune-mediated colitis has been associated with the administration of atezolizumab. Management guidelines for diarrhea or colitis are provided in [Table 3](#).

All events of diarrhea or colitis should be thoroughly evaluated for other more common etiologies. For events of significant duration or magnitude or associated with signs of systemic inflammation or acute-phase reactants (e.g., increased C-reactive protein, platelet count, or bandemia): Perform sigmoidoscopy (or colonoscopy, if appropriate) with colonic biopsy, with three to five specimens for standard paraffin block to check for inflammation and lymphocytic infiltrates to confirm colitis diagnosis.

Appendix 11

Risks Associated with Atezolizumab and Guidelines for Management of Adverse Events Associated with Atezolizumab (cont.)

Table 3 Management Guidelines for Gastrointestinal Events (Diarrhea or Colitis)

Event	Management
Diarrhea or colitis, Grade 1	
 • Continue atezolizumab. • Initiate symptomatic treatment. • Endoscopy is recommended if symptoms persist for >7 days. • Monitor closely.
Diarrhea or colitis, Grade 2	
 • Withhold atezolizumab for up to 12 weeks after event onset. ^a • Initiate symptomatic treatment. • Patient referral to GI specialist is recommended. • For recurrent events or events that persist > 5 days, initiate treatment with 1–2 mg/kg/day oral prednisone or equivalent. • If event resolves to Grade 1 or better, resume atezolizumab. ^b • If event does not resolve to Grade 1 or better while withholding atezolizumab, permanently discontinue atezolizumab and contact Medical Monitor. ^c
Diarrhea or colitis, Grade 3	
 • Withhold atezolizumab for up to 12 weeks after event onset. ^a • Refer patient to GI specialist for evaluation and confirmatory biopsy. • Initiate treatment with 1–2 mg/kg/day IV methylprednisolone or equivalent and convert to 1–2 mg/kg/day oral prednisone or equivalent upon improvement. • If event resolves to Grade 1 or better, resume atezolizumab. ^b • If event does not resolve to Grade 1 or better while withholding atezolizumab, permanently discontinue atezolizumab and contact Medical Monitor. ^c

GI = gastrointestinal.

^a Atezolizumab may be withheld for a longer period of time (i.e., > 12 weeks after event onset) to allow for corticosteroids (if initiated) to be reduced to ≤ 10 mg/day oral prednisone or equivalent. The acceptable length of the extended period of time must be agreed upon by the investigator and the Medical Monitor.

^b If corticosteroids have been initiated, they must be tapered over ≥ 1 month to ≤ 10 mg/day oral prednisone or equivalent before atezolizumab can be resumed.

^c Resumption of atezolizumab may be considered in patients who are deriving benefit and have fully recovered from the immune-mediated event. Patients can be re-challenged with atezolizumab only after approval has been documented by both the investigator (or an appropriate delegate) and the Medical Monitor.

Appendix 11

Risks Associated with Atezolizumab and Guidelines for Management of Adverse Events Associated with Atezolizumab (cont.)

Table 3 Management Guidelines for Gastrointestinal Events (Diarrhea or Colitis) (cont.)

Event	Management
Diarrhea or colitis, Grade 4	
 • Permanently discontinue atezolizumab and contact Medical Monitor. ^c • Refer patient to GI specialist for evaluation and confirmation biopsy. • Initiate treatment with 1–2 mg/kg/day IV methylprednisolone or equivalent and convert to 1–2 mg/kg/day oral prednisone or equivalent upon improvement. • If event does not improve within 48 hours after initiating corticosteroids, consider adding an immunosuppressive agent. • If event resolves to Grade 1 or better, taper corticosteroids over ≥ 1 month.

GI = gastrointestinal.

- ^a Atezolizumab may be withheld for a longer period of time (i.e., > 12 weeks after event onset) to allow for corticosteroids (if initiated) to be reduced to ≤ 10 mg/day oral prednisone or equivalent. The acceptable length of the extended period of time must be agreed upon by the investigator and the Medical Monitor.
- ^b If corticosteroids have been initiated, they must be tapered over ≥ 1 month to ≤ 10 mg/day oral prednisone or equivalent before atezolizumab can be resumed.
- ^c Resumption of atezolizumab may be considered in patients who are deriving benefit and have fully recovered from the immune-mediated event. Patients can be re-challenged with atezolizumab only after approval has been documented by both the investigator (or an appropriate delegate) and the Medical Monitor.

ENDOCRINE EVENTS

Thyroid disorders, adrenal insufficiency, diabetes mellitus, and pituitary disorders have been associated with the administration of atezolizumab. Management guidelines for endocrine events are provided in [Table 4](#).

Patients with unexplained symptoms such as headache, fatigue, myalgias, impotence, constipation, or mental status changes should be investigated for the presence of thyroid, pituitary, or adrenal endocrinopathies. The patient should be referred to an endocrinologist if an endocrinopathy is suspected. Thyroid-stimulating hormone (TSH) and free triiodothyronine and thyroxine levels should be measured to determine whether thyroid abnormalities are present. Pituitary hormone levels and function tests (e.g., TSH, growth hormone, luteinizing hormone, follicle-stimulating hormone, testosterone, prolactin, adrenocorticotrophic hormone [ACTH] levels, and ACTH stimulation test) and magnetic resonance imaging (MRI) of the brain (with detailed pituitary sections) may help to differentiate primary pituitary insufficiency from primary adrenal insufficiency.

Appendix 11

Risks Associated with Atezolizumab and Guidelines for Management of Adverse Events Associated with Atezolizumab (cont.)

Table 4 Management Guidelines for Endocrine Events

Event	Management
Asymptomatic hypothyroidism	
 • Continue atezolizumab. • Initiate treatment with thyroid replacement hormone. • Monitor TSH weekly.
Symptomatic hypothyroidism	
 • Withhold atezolizumab. • Initiate treatment with thyroid replacement hormone. • Monitor TSH weekly. • Consider patient referral to endocrinologist. • Resume atezolizumab when symptoms are controlled and thyroid function is improving.
Asymptomatic hyperthyroidism	
TSH ≥ 0.1 mU/L and < 0.5 mU/L:
 
 • Continue atezolizumab. • Monitor TSH every 4 weeks. 
TSH < 0.1 mU/L:
 
 • Follow guidelines for symptomatic hyperthyroidism.
Symptomatic hyperthyroidism	
 • Withhold atezolizumab. • Initiate treatment with anti-thyroid drug such as methimazole or carbimazole as needed. • Consider patient referral to endocrinologist. • Resume atezolizumab when symptoms are controlled and thyroid function is improving. • Permanently discontinue atezolizumab and contact Medical Monitor for life-threatening immune-mediated hyperthyroidism. <small>c</small>

MRI=magnetic resonance imaging; TSH=thyroid-stimulating hormone.

- ^a Atezolizumab may be withheld for a longer period of time (i.e., > 12 weeks after event onset) to allow for corticosteroids (if initiated) to be reduced to ≤ 10 mg/day oral prednisone or equivalent. The acceptable length of the extended period of time must be agreed upon by the investigator and the Medical Monitor.
- ^b If corticosteroids have been initiated, they must be tapered over ≥ 1 month to ≤ 10 mg/day oral prednisone or equivalent before atezolizumab can be resumed.
- ^c Resumption of atezolizumab may be considered in patients who are deriving benefit and have fully recovered from the immune-mediated event. Patients can be re-challenged with atezolizumab only after approval has been documented by both the investigator (or an appropriate delegate) and the Medical Monitor.

Appendix 11

Risks Associated with Atezolizumab and Guidelines for Management of Adverse Events Associated with Atezolizumab (cont.)

Table 4 Management Guidelines for Endocrine Events (cont.)

Event	Management
Symptomatic adrenal insufficiency, Grade 2–4	
 • Withhold atezolizumab for up to 12 weeks after event onset.^a • Refer patient to endocrinologist. • Perform appropriate imaging. • Initiate treatment with 1–2 mg/kg/day IV methylprednisolone or equivalent and convert to 1–2 mg/kg/day oral prednisone or equivalent upon improvement. • If event resolves to Grade 1 or better and patient is stable on replacement therapy, resume atezolizumab.^b • If event does not resolve to Grade 1 or better or patient is not stable on replacement therapy while withholding atezolizumab, permanently discontinue atezolizumab and contact Medical Monitor.^c
Hyperglycemia, Grade 1 or 2	
 • Continue atezolizumab. • Initiate treatment with insulin if needed. • Monitor for glucose control.
Hyperglycemia, Grade 3 or 4	
 • Withhold atezolizumab. • Initiate treatment with insulin. • Monitor for glucose control. • Resume atezolizumab when symptoms resolve and glucose levels are stable.

MRI=magnetic resonance imaging; TSH=thyroid-stimulating hormone.

^a Atezolizumab may be withheld for a longer period of time (i.e., > 12 weeks after event onset) to allow for corticosteroids (if initiated) to be reduced to ≤10 mg/day oral prednisone or equivalent. The acceptable length of the extended period of time must be agreed upon by the investigator and the Medical Monitor.

